13.3 Stratification Factors

No stratified analysis is foreseen.

13.4 Analysis of Secondary Endpoints

Proportions (will be calculated and reported with their 95% confidence interval (binomial law).

Progression-free and overall survivals will be analyzed using the Kaplan-Meier method. The median survival rates will be reported with a 95% confidence interval. Median follow-up will be calculated using the reverse Kaplan-Meier method.

Duration of response will be described in responding subjects using descriptive statistics (median, extreme values, etc.).

The predictive value of biomarkers will be investigated using multivariate logistic regression (when evaluating impact on tumour response) or a Cox Proportional hazard model (when evaluating impact on time to tumour response) after checking for the proportional hazards assumption.

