1.3. Study design and calendar

This is single-arm phase 2 clinical trial based on two-stage Simon's design.

- Beginning of inclusions : September 2010
- Inclusion period: September 2010 to September 2012 (2 years)
- Length of patient participation: 2 years
- Study length: 4 years.

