b: Serum or urine test 7 days prior to the first dose of GDC-0449 administration. Pregnancy test must be administered 24 hours prior to the start of therapy (serum) and at least once every month thereafter (serum or urine).
c: Off-treatment evaluation.
d: Tumor measurements are repeated every 8 weeks. Documentation (radiology) must be provided for patients removed from study for progressive disease. Beyond 48 months of treatment without evidence of progressive disease, radiological tumor assessment will be performed every 3 months.
e: After 6 cycles, blood test will be performed every two weeks (week 2 and week 4). Beyond 48 months of treatment blood test will be performed every 3 months.
f: After 25 cycles, physical exam (vital signs, weight, performance status) will be performed/evaluated every 3 months
Baseline evaluations are to be conducted within one week prior to start of protocol therapy.
Scans and X-rays must be done ≤ 4 weeks prior to the start of therapy.

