11.1.5 Duration of Response

Duration of overall response: The duration of overall response is measured from the time measurement criteria are met for CR or PR (whichever is first recorded) until the first date that recurrent or progressive disease is objectively documented (taking as reference for progressive disease the smallest measurements recorded since the treatment started).

The duration of overall CR is measured from the time measurement criteria are first met for CR until the first date that recurrent disease is objectively documented.

Duration of stable disease: Stable disease is measured from the start of the treatment until the criteria for progression are met, taking as reference the smallest measurements recorded since the treatment started.

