14.2.3. Handling of missing data

The monitoring of data for adverse events will be carried out regularly in order to effectively limit the amount of missing data likely to prevent or hamper trial implementation and analysis.

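### Duration of response is given a plain median and extremes with no rule for responses that have not ended, so it can be understated if any are ongoing or censored at analysis

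*Combined protocol and SAP*

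**What the plan says.** Section 13.4 gives the whole analysis of duration of response in one sentence: "Duration of response will be described in responding subjects using descriptive statistics (median, extreme values, etc". For the other time-to-event quantities the same section is explicit: "Progression-free and overall survivals will be analyzed using the Kaplan-Meier method", with reverse Kaplan-Meier for follow-up.

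Section 11.1.5 starts the clock when CR or PR criteria are first met and runs it "until the first date that recurrent or progressive disease is objectively documented". It does not say what happens to a response that has not ended, to a responder who dies without documented progression, or to one who starts another therapy. Section 11.1.6, by contrast, counts death as a PFS event.

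The section on missing data does not fill the gap. It says only that "The monitoring of data for adverse events will be carried out regularly in order to effectively limit the amount of missing data" likely to hamper the trial. Section 11.1.4 carries over the RECIST instruction that the analysis plan must deal with missing assessments when determining response and progression, but section 13 contains no such rule.

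On timing, section 1.3 gives "Inclusion period: September 2010 to September 2012 (2 years", "Length of patient participation: 2 years" and "Study length: 4 years". No data cut-off is stated for duration of response. The footnotes to the study calendar provide for long progression-free follow-up: "Beyond 48 months of treatment without evidence of progressive disease, radiological tumor assessment will be performed every 3 months".

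**The concern.** A response without documented progression at analysis is right-censored. A plain median and range can handle it in only two ways: count the observed length as the full length, or leave the patient out. Either makes the reported maximum too low when the longest response is still running, and either can pull the median down.

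Ongoing or censored responses are plausible. The calendar allows for patients progression-free beyond 48 months (these may be stable-disease patients as well as responders). Section 5.3 also lets treatment stop for toxicity, intercurrent illness or patient withdrawal, so documentation of progression may be missing before any cut-off.

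What is at stake is one descriptive figure that the plan commits to report, and its comparability with the Kaplan-Meier results beside it.

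**Working it through.** The plan states no figure for duration of response, so there is none to reproduce. The check asks when the plain median goes wrong, and by how much.

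**Inputs from the documents.** Inclusion 24 months, participation 24 months per patient, study 48 months (section 1.3). The planned end is therefore 48 − 24 = 24 months after the last inclusion.

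**Assumptions, not in the documents.** Exponential durations; uniform accrual; response onset 2–6 months after treatment start; administrative censoring only. True medians run from 8.8 to 24 months. The value 8.8 is the median response duration that section 2.2 reports for basal-cell carcinoma, used only as a reference point.

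**Step 1: when counting ongoing responses as ended is harmless.** If a response of true length *T* is observed up to censoring time *C*, the plain median is the *t* that solves

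P(T > t) × P(C > t) = 0.5.

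If every *C* exceeds the true median, the second factor is 1 there and the median is unchanged. With 24 months of participation and onset no later than month 6, the shortest *C* is 24 − 6 = 18 months. True medians up to about 18 months are therefore safe at the planned end.

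**Step 2: plain median by cut-off.** Simulation, 100,000 responders per scenario, followed to the cut-off. Each cell shows ongoing counted as ended / ongoing dropped, in months.

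| True median | Cut 6 months after last inclusion | Cut 12 months after | Cut 24 months after (planned end) |
|---|---|---|---|
| 8.8 | 6.3 / 4.8 | 8.4 / 6.1 | 8.8 / 7.7 |
| 12 | 7.5 / 5.5 | 10.3 / 7.0 | 12.0 / 9.2 |
| 18 | 9.0 / 6.1 | 12.6 / 7.8 | 18.1 / 11.1 |
| 24 | 10.0 / 6.4 | 14.1 / 8.4 | 21.6 / 12.2 |

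The Kaplan-Meier median was within 0.1 month of the truth in every cell.

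- Early cut, counted as ended: from (8.8 − 6.3)/8.8 = 28% low to (24 − 10.0)/24 = 58% low.
- Planned end, counted as ended: no material loss up to a true median of 18 months; (24 − 21.6)/24 = 10% low at 24 months.
- Dropped: low at every cut-off. For a true 12 months at the planned end, (12 − 9.2)/12 = 23% low.

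**Step 3: if each patient is followed for exactly 24 months.** *C* then lies between 18 and 22 months. True medians up to 18 months are still recovered. For a true median of 24 months, try *t* = 18.6: 2^(−18.6/24) = 0.584 and (22 − 18.6)/4 = 0.85, product 0.50. The plain median is about 18.6 months, or (24 − 18.6)/24 ≈ 23% low.

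**Step 4: the maximum.** This needs no model. If the longest response is ongoing, its observed length is a lower bound, and reporting it unmarked as the maximum understates it.

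**The case against.** The strongest reply is that section 13.4 is silent rather than wrong. It describes duration in responding subjects, does not say that ongoing responses count as ended, and does not restrict the summary to completed ones. That stands: the defect is an omission.

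The second reply is that on the plan's own calendar the median is robust. This also stands, for counting ongoing durations at their observed length, up to true medians of about 18 months. A reader might infer a large bias in all cases. With only 3–20 months of follow-up after response, for example, the equation in Step 1 gives a plain median of 6.3 months for a true 9 and 7.2 for a true 12. That window belongs to an early data cut. It does not match section 1.3, and the documents schedule no such cut for this analysis.

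Third, responders may be few. The 20% and 40% design rates include stable disease, no response rate is assumed, and plain description of a handful of durations is defensible. This is fair, but description still has to show which durations are ongoing.

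What the replies do not remove is the understated maximum, the loss when ongoing responders are dropped, and early censoring through withdrawal or loss to follow-up, which the calculations above leave out.

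**Conclusion.** The point holds as a gap in specification with a conditional effect. Duration of response is a time-to-event quantity that receives a plain median and extremes and no rule for responses without an end date, while PFS and OS beside it use Kaplan-Meier.

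- The maximum is too low whenever the longest response is ongoing.
- The median is too low if ongoing responders are dropped, or if they are counted as ended and censoring falls before the true median, as with an early data cut, withdrawal or loss to follow-up.
- At the planned 4-year end, counting ongoing durations as ended leaves the median essentially intact for true medians up to about 18 months. At 24 months it is about 10% low with follow-up to study end, or about 23% low with exactly 24 months per patient.

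These sizes rest on exponential durations, onset at 2–6 months and administrative censoring only. The documents do not support the stronger reading that the plan treats ongoing responses as ended and so necessarily understates duration.

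Importance is low. Duration of response is not among the objectives in sections 1.1 and 1.2, and the two-stage decision rule in 13.2 does not use it.

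**What to change.** Replace the sentence in section 13.4 with text to this effect: *Duration of response will be estimated by Kaplan-Meier among confirmed responders. Responders without progression will be censored at their last adequate tumour assessment. The median with 95% confidence interval, the number of events and the number of ongoing responses will be reported.*

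Add two rules. State how death without documented progression is handled, consistently with the PFS definition in section 11.1.6, and align section 11.1.5 with it. State how the start of a new therapy is handled in this analysis.

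If responders are few, list each duration and mark those still ongoing.

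The cost is a few sentences, using a method the section already names and data already collected. The downside is that the Kaplan-Meier median may not be reached. With an assumed 8 responders and the short 3–20 month window, that happened in 15% of simulated trials for a true median of 9 months and in 30% for 12 months. The listing covers that case.

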13.5 Reporting and Exclusions

13.5.1. Evaluation of toxicity.

All patients will be evaluable for toxicity from the time of their first treatment with GDC-0449.

13.5.2. Evaluation of response.

All patients included in the study will be assessed for response to treatment, even if there are major protocol treatment deviations or if they are ineligible.

Each patient will be assigned one of the following categories: 1) complete response, 2) partial response, 3) stable disease, 4) progressive disease, 5) early death from malignant disease, 6) early death from toxicity, 7) early death because of other cause, or 9) unknown (not assessable, insufficient data). [Note: By arbitrary convention, category 9 usually designates the “unknown” status of any type of data in a clinical database.]

All of the patients who met the eligibility criteria AND who received at least one complete or two incomplete cycles of the drug will be included in the main analysis of the response rate.

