11.1.1 Definitions

Evaluable for toxicity: All patients will be evaluable for toxicity from the time of their first treatment with GDC-0449.

Evaluable for objective response: Only those patients who have measurable disease present at baseline and have received at least one complete or two incomplete cycle of therapy will be included in the main analysis of the response rate.

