13.2 Sample Size/Accrual Rate

The data from the literature about survival of patients with advanced chondrosarcomas are almost non-existent. However, some studies confirm that the prognosis of patients with metastatic chondrosarcomas is poor and similar to that observed in metastatic soft-tissue tumors with median survival ranging from 7 to 17 months ([Dickey et al., 2004](#); [Ries et al., 2007](#); [Giuffrida et al., 2009](#)). Therefore, we believe that a 6 months clinical benefit rate of 40% is a reasonable objective in this setting. This objective was also chosen by American investigators (SARC) in a phase 2 trial of perifosine in patients with chemo-insensitive sarcomas (including chondrosarcomas).

We rely on an optimal two-stage Simon's design (Simon, 1989). Based on the following hypotheses under GDC-0449 treatment:

- 20% non-progression rate (null hypothesis),
- 40% acceptable non-progression rate (alternative hypothesis),
- 10% type I error rate,
- 90% power,

a total of 37 assessable subjects will be necessary, with 17 assessable subjects recruited to the first stage.

Stage 1: Following the inclusion of the first 17 assessable patients, if 3 or less patients are progression-free (complete response, partial response or stable disease), the study would be terminated early. Otherwise, the second group of 20 subjects will be recruited.

Stage 2: If at the end of recruitment, 11 patients or more are progression-free (out of the 37 evaluable patients), GDC-0449 would be considered worthy of further testing in this disease.

To be evaluable, a subject must meet the eligibility criteria AND have received at least one complete or two incomplete cycles of GDC-0449 AND at least one disease measurement recorded not less than eight weeks after treatment onset.

Given the disease is rare and the absence of standard treatment in this indication, inclusion will not be suspended after the recruitment of the first 17 patients. Inclusion will be pursued, while data on the first 17 patients will be analyzed.

In order to account for not evaluable patients (+/- 20%), **45 patients will be recruited.**

The anticipated accrual rate is 2-3 patients/months.

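### The main denominator requires one full or two partial cycles, so patients who die or stop for good in cycle 1 are left out instead of being counted as failures

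*Combined protocol and SAP*

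**What the plan says.** Section 13.5.2 opens with an all-patient principle: patients included in the study "will be assessed for response to treatment, even if there are major protocol treatment deviations or if they are ineligible". It lists outcome categories that include early death from disease, from toxicity and from other causes, and an unknown category. Its last sentence then restricts the main analysis to eligible patients "who received at least one complete or two incomplete cycles of the drug will be included in the main analysis of the response rate".

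The same exposure condition stands in three other places:

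- Section 11.1.1: only patients with measurable disease at baseline who "have received at least one complete or two incomplete cycle of therapy will be included in the main analysis of the response rate".
- Section 13.2, for the Simon decision: a subject must be eligible and "have received at least one complete or two incomplete cycles of GDC-0449", and must also have a disease measurement eight weeks or more after treatment start.
- The synopsis, under efficacy evaluations: both conditions, with an exception for early progression that follows the measurement clause.

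Section 13.1 defines failure at six months as death, or being alive with progression. Section 5.1 sets the cycle at 28 days. Section 13.2 sizes the trial on evaluable patients: "a total of 37 assessable subjects will be necessary, with 17 assessable subjects recruited to the first stage". The trial stops at 3 or fewer successes in 17, and the drug is worth further testing at 11 or more in 37. Forty-five patients are to be recruited.

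**The concern.** A patient who stops for good during the first 28 days has one partial cycle and can never have a second. Whether that patient enters the main denominator is thus settled by what happens after treatment starts, and often by the outcome itself. Deaths in cycle 1 are failures under section 13.1 and have their own categories in section 13.5.2, but the last sentence of 13.5.2 takes them out of the main analysis. Nothing in the plan says that the early-death or unknown categories count as failures in that analysis, and no rate in all treated patients is planned beside it.

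Two results are exposed: the best overall response rate (13.5.2 and 11.1.1), and the 6-month benefit rate with its stop and go rules (13.2). Patients who survived and tolerated cycle 1 would stand in for all patients who started treatment.

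**Working it through.** **1. Reproduce the design.** Inputs from section 13.2: null rate 20%, alternative 40%, "10% type I error rate", 90% power, 17 + 20 patients. With p the success rate per evaluable patient:

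P(go) = sum over x = 4 to 17 of Bin(x; 17, p) × P(Bin(20, p) ≥ 11 − x)

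This gives 0.0948 at p = 0.20 and 0.903 at p = 0.40. The probability of stopping at stage 1 under the null is 0.549. A full search for the optimal design returns the same 3/17 and 10/37. The sample size itself is right.

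**2. Who is dropped.** Setting the sections side by side:

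| Event in the first 28 days | Status under 13.1 | In the main denominator? |
|---|---|---|
| Death | Failure | No |
| Progression, treatment stopped for good | Failure | No |
| Progression, cycle 1 completed | Failure | Passes the exposure condition |
| Stop for toxicity | Depends on status at 6 months | No |

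**3. How many deaths.** The documents give no early death rate. Assumption: constant hazard at the median survival of 7 to 17 months quoted in section 13.2. With 28 days = 0.92 months, x = 1 − exp(−ln 2 × 0.92 / median):

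- median 17 months: x = 3.7%, or 1.7 of 45
- median 7 months: x = 8.7%, or 3.9 of 45

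**4. Effect on the Simon decision.** Assumption: 20% is the true rate in all treated patients, and those removed are all failures (here they are deaths). The rate in the kept set is 0.20 / (1 − x).

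| Removed | Rate in kept set | P(go) = type I error | P(stop at stage 1) |
|---|---|---|---|
| 0% | 20.0% | 0.095 | 0.549 |
| 3.7% | 20.8% (0.2076) | 0.116 | 0.517 |
| 8.7% | 21.9% (0.2191) | 0.154 | 0.470 |

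**5. Effect on best overall response.** Illustration with 4 responders: 4/45 = 8.9% in all patients, against 4/43.3 = 9.2% to 4/41.1 = 9.7% in the kept set.

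**6. Effect of changing the denominator without changing the cut-off.** With the 3/17 stage-1 rule kept and 45 patients in total, the same exact calculation gives:

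- 11 or more of 45: type I error 0.215
- 13 or more of 45: type I error 0.087, power 0.923

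**The case against.** Several points on the other side stand, and they limit the claim.

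- **The exposure condition is not the only cause.** Section 13.2 also requires a measurement at eight weeks or later. A patient dead by day 28 cannot have one, so every death in step 4 is already removed by that rule. The rise in type I error belongs to both rules together. Only sections 13.5.2 and 11.1.1 have the exposure condition without the scan condition, and there the effect is the small one in step 5.
- **Not everyone removed is a failure.** A reader might infer that all dropped patients are non-responders. For the 6-month endpoint the documents do not support this. Section 13.1 does not require the patient to be on treatment, and section 7.8 keeps a patient in follow-up after treatment is stopped for good. A patient who stops early for toxicity may still be progression-free at six months.
- **Progression alone does not remove a patient.** Someone who progresses but completes cycle 1 meets the exposure condition. The first scheduled tumour assessment is at eight weeks, so progression documented by day 28 should be uncommon. The synopsis exception could be read as covering both conditions, but its position ties it to the scan clause. It names neither death nor toxicity, and it is absent from 11.1.1, 13.2 and 13.5.2.
- **The null rate may refer to evaluable patients.** Section 13.2 sizes the trial on assessable subjects and gives no source for 20%. Type I error rises only if 20% is taken as the rate in all treated patients.
- **The early death rate is probably generous.** Entry requires life expectancy above three months and ECOG 2 or better.
- **Some information survives.** Every included patient receives a category, so an all-patient rate can be derived, and PFS and OS run from treatment start without this filter.

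None of this changes the direction of the bias or removes the conflict inside section 13.5.2.

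**Conclusion.** The concern holds for patients who die, or who stop for good with progression or toxicity, during the first 28 days. Followed as written, the plan leaves them out of the main denominator and biases both rates upward. Toxicity stops add to the bias only where the patient has progressed, died or has unknown status at six months.

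Under the two assumptions stated (20% as the all-treated null rate; constant hazard, at the upper end of what is plausible), type I error is about 11.6% to 15.4% instead of 9.5%, an effect shared with the 8-week rule. For best overall response the shift is under one percentage point in the example.

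A reader might go further and treat the whole allowance of about 20% non-evaluable patients as early failures, which would give 25% in the kept set and a type I error of 0.285. That is only a ceiling: the documents do not say why patients would be non-evaluable, and ineligibility or other reasons unrelated to outcome would count too.

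**What to change.** In 13.5.2, 11.1.1, 13.2 and the synopsis:

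1. Make eligible patients who received at least one dose the main denominator.
2. Count progression, early death and unknown status as non-response or failure. For the 6-month endpoint, classify patients who stop early but have a known 6-month status by that status.
3. Lift the 8-week measurement condition for these patients as well. Deleting the exposure condition alone would not bring them back into the Simon decision.
4. Match the decision rule to the denominator. Either apply 3/17 and 11/37 to the first 17 and first 37 such patients, or use all 45 and restate the final cut-off as 13 or more. Keeping 11 with 45 patients would do more harm than the problem being repaired (step 6).
5. Keep the current evaluable set as a labelled sensitivity analysis.

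The cost is revised wording in four places, a restated decision rule and slightly less favourable rates. No new data are needed.
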